# 5. Family Environment Scale (FES)

- ✤ As an additional measure of the family environment, we will use the Moos Family Environment Scale (FES) (Moos, 1985; Moos, 1976).
- The FES assesses the quality of interpersonal relationships among family members. This scale consists of 90 true-false items to be completed by the parents. This measure permits an assessment of the degree of stress in the family environment and of parental discord.
- Administered at beginning of study to characterize the groups and ensure their similarity.

# 6. DSM-IV Global Assessment of Functioning (GAF)

- The GAF (APA, 1994) will assess global functioning using a scale from 1 (worst) to 100 (best). Guidelines and examples of how to use this scale are provided with the scale.
- This clinician rated scale will be used at baseline visit to characterize the sample, at each of the 12 weekly visits to assess change, and at endpoint, to assess the impact of treatment on global functioning.

# **7. Pediatric Quality of Life Enjoyment and Satisfaction Questionnaire (PQ-LES-Q)** (Endicott, 2006)

✤ A 15-item rating scale to assess the degree of life enjoyment and satisfaction for children. Baseline and endpoint.

# 8. Neuropsychological Tests/Cognitive Evaluation

IQ Testing: At study beginning, subjects will complete a brief cognitive screen. The scales we will use meet the demand for quick reliable measures of intelligence in clinical, educational and research settings. These tests will provide estimates of verbal and nonverbal ability respectively, as well as the direct measure of Full Scale IQ. This portion of the cognitive evaluation will take

approximately 30 minutes to complete. In the unlikely event that a subject's estimated IQ is below 70, the subject will not be eligible to participate in the study. Depending upon the subject's age, the cognitive screen will consist of:

- **Subjects age 5:** Verbal Knowledge, Riddles, and Matrices subtests of the Kaufman Brief Intelligence Test, Second Edition (KBIT-2)(Kaufman & Kaufman, 2004)
- Subjects ages 6-12: Vocabulary and Matrices subtests of the Wechsler Abbreviated Scale of Intelligence (WASI)(Wechsler, 2003)
- Cognitive Functioning Testing: At screening and endpoint, to assess the impact of treatment on cognition, we will assess basic intellectual and cognitive functions purported to be deficient in patients with bipolar disorder. Cognitive deficits that have been observed in bipolar disorder may reflect dysfunction in the frontal subcortical circuits that support aspects of attention, executive functions processing speed, memory and learning (Bearden, 2001). The neuropsychological battery we have developed to assess these functions includes both published clinical measures with large, normative samples and experimental measures with strong empirical evidence of validity. This neuropsychological battery, which has been used widely in clinical trials and family studies in our office, has been well tolerated. The testing will take approximately 25 minutes to complete. The ageappropriate testing will include:
  - Subjects age 5: Symbol Search and Coding subtests of the Wechsler Preschool and Primary Scale of Intelligence (WPPSI-III) (Wechsler & Sattler, 2002) to measure processing speed
  - Subjects ages 6-12: Digit Span and Coding subtests from the Wechsler Intelligence Scale for Children-Fourth Edition (WISC-IV) (Wechsler, 2003) to measure working memory and processing speed

The working memory scale will be omitted for subjects who are 5 years of age, as we do not have an age-appropriate scale available.

# Efficacy Measures

The primary efficacy measures are the mean change from baseline to endpoint in the Young Mania Rating Scale (YMRS) total score and the Children's Depression Rating Scale (CDRS). These will be administered by the clinician at Screening Visit, Baseline Visit, at each of the weekly visits and endpoint.

# 1. Young Mania Rating Scale (YMRS)

- The YMRS (Young, 1978) consists of 11 items rated on a scale from 0 (symptom not present) to 4 (symptom extremely severe).
- Items 5, 6, 8, and 9 are rated on a scale from 0 (symptom not present) to 8 (symptom extremely severe). These items assess irritability, speech, content and disruptive/aggressive behavior) and are given extra weight in the overall score.
- The YMRS score ranges from 0-60. Questions are asked about the last week. This scale is generally accepted as the main outcome measure in studies of pediatric bipolar disorder and is linked directly to the core symptoms of mania.

Collected at the Screening Visit, Baseline Visit (only subjects with a YMRS score of 20 or greater, but not above 40, are included), at each of the weekly visits and at endpoint to assess the impact of treatment on manic symptoms.

# 2. Children's Depression Rating Scale (CDRS)

- The CDRS (Poznanski, 1985) is modeled after the Hamilton Depression Rating Scale for adults, but includes questions relevant to youth, such as questions about school, family and peer functioning.
- This is a clinician-rated instrument with 17 items scored on a 1 to 5 or 1 to 7 scale. A rating of 1 indicates normal, thus the minimum score is 17. The maximum score is 113. Scores of 20-30 suggest borderline depression. Scores of 40-60 indicate moderate depression.
- This scale is generally accepted as the main outcome in studies assessing childhood depression and is linked directly to the core symptoms of depression.
- Collected at the Screening Visit, Baseline Visit, at each of the weekly visits and at endpoint.

# **3. Hamilton Depression Rating Scale**

- The HAM-D is a clinician rated instrument that measures the severity of depressive symptoms.
- ✤ This is a clinican-rated instrument with 21 items scored on a 0 to 4 scale.
- Collected at the Screening Visit, Baseline Visit, at each of the weekly visits and at endpoint.

As secondary measures to assess severity and improvement relative to baseline for mania, depression and common comorbid conditions, we will use other measures including: a DSM-IV Mania Symptom Checklist; the Attention Deficit Hyperactivity Disorder (ADHD) Rating Scale; the Brief Psychiatric Rating Scale (BPRS); and the NIMH Clinical Global Impression scale (CGI) (Severity, Improvement and Efficacy Index) for mania, depression, Bipolar Disorder overall, ADHD, Oppositional Defiant Disorder and Anxiety. Most of these scales will be administered at baseline visit, at each of the weekly visits and at endpoint by the clinician to assess the impact of treatment on ADHD, anxiety, and to have other measures related to the impact of treatment on bipolar disorder. We will also have the subject's parent/guardian complete the Social Responsiveness Scale (SRS) and the Impact on Family Scale at baseline and endpoint, as well as the Behavior Rating Inventory of Executive Function – Parent Form (BRIEF) at the baseline and endpoint visits.

# 1. DSM-IV Mania Symptom Checklist

- This Checklist is adapted from the DSM-IV mania diagnostic criteria with items for each symptom of mania. Each item is scored 0 to 3 ranging (0=never or rarely; 1=sometimes; 2=often; 3=very often).
- Collected at baseline visit, at each of the weekly visits and at endpoint as an additional measure of manic symptoms.

# 2. Attention Deficit Hyperactivity Disorder (ADHD) Rating Scale

- The ADHD Rating Scale is an 18 item scale with 1 item for each of the 18 DSM-IV ADHD symptoms. Each item is scored 0 to 3 (0=never or rarely; 1=sometimes; 2=often; 3=very often).
- Collected at baseline visit, middle and endpoint to assess the impact of treatment on ADHD symptoms, which often co-occur with pediatric bipolar disorder.

# 3. Brief Psychiatric Rating Scale (BPRS)

- The Brief Psychiatric Rating Scale (BPRS) is a common scale used to assess overall psychopathology (Overall and Pfefferbaum, 1982). The scale consists of 18 items; each rated on a scale from 1 (symptom not present) to 7 (symptom extremely severe).
- Collected at Baseline Visit and at endpoint to assess the impact of treatment on depression, anxiety hallucinations and unusual behavior, which often co-occur with pediatric bipolar disorder.

## 4. Social Responsiveness Scale (SRS)

- The SRS is a 65 item rating scale completed by the parent or guardian. This scale measures the severity of autism spectrum symptoms as they occur in natural social settings.
- Collected at Screening and Endpoint visits as assessment of symptoms and capacities associated with social interaction.

# 5. NIMH Clinical Global Improvement scale (CGI)

- The CGI is a measure of illness severity adapted for specific disorders. It allows rating of mania, depression and overall bipolar disorder illness, as well as other conditions frequently comorbid with bipolar disorder.
- The severity score ranges from 1 (normal, not at all ill) to 7 (among the most extremely ill patients). The improvement score ranges from 1 (very much improved) to 7 (very much worse).
- Collected at Baseline Visit, at each of the weekly visits and at endpoint as an accepted measure of clinician rated improvement to assess the impact of treatment on bipolar disorder and other comorbid conditions.

#### 6. Impact on Family Scale

- The Impact on Family Scale measures the effects of chronic childhood illness on quality of life within a family, in four dimensions: a) financial burden, b) disruption of social interaction, c) psychological burden on the caregiver, and d) coping strategies used by the family.
- This scale will be used at screening and endpoint, completed by the parent of the study subject.

#### 7. Behavior Rating Inventory of Executive Function – Parent Form (BRIEF)

- The BRIEF is an 86-item rating scale to assess level of executive function deficits (Roth et al., 2004). It is completed by the subject's parent/guardian.
- Collected at Baseline Visit, middle visit and at endpoint.

# Safety Measures

- Adverse Experiences: to record any adverse health events experienced during the study along with duration, severity, cause, remedy, and outcome.
- Columbia Suicide Severity Rating Scale (C-SSRS): to assess initial and emergent suicidality.

# 9. DATA ANALYSIS

# A. Statistical Analysis

90 subjects will be randomized (1:1:1) into one of three treatment groups: inositol, omega-3 fatty acids, or inositol plus omega-3 fatty acids. Subjects will be block-randomized to ensure equal age and gender distribution between groups. Because this is a randomized trial following subjects over a short period of time missing data are not expected to impact our analyses such that standard statistical analyses will be employed. Changes in ratings of mania within and between study groups over time will be tested with repeated measures analysis of covariance using the statistical software package STATA. All analyses will be intention to treat (ITT) with the last observation carried forward for subjects that do not complete the trial or are dropped from the study according to the exit criteria described earlier.

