In one of three published treatment studies of children to date Voigt et al, reported that omega-3 fatty acids are ineffective for ADHD, but were well tolerated (Voigt, 2001). Nemets et al randomized 28 children to omega-3 fatty acids or placebo and found improvement in depression as measured by the Childrens Depression Rating Scale (CDRS). The third study in children is our own preliminary study and demonstrates a modest improvement in supplemented youth. In this study, subjects (N=19) experienced a statistically significant but modest  $8.9\pm2.9$  point reduction in the YMRS scores after 8 week open label treatment with omega-3 fatty acids (baseline YMRS=28.9±10.1; endpoint YMRS=19.1±2.6, p<0.001). Adverse events were few and mild, and of the 20 subjects recruited, there were only 4 drop outs due to ineffectiveness and none dropped out due to adverse events. Although a decrease in the CDRS was noted, subjects remained in the psychopathologic range. The mean dose of omega-3 fatty acid was  $2965\pm991 \text{ mg}$  / day (range 1290 - 4300, or 3-10 capsules). There was no benefit seen to increasing the dose beyond 2 grams per day. Laboratory analyses did not reveal any significant baseline-endpoint differences in chemistries, hematology, prolactin, glucose, or lipids. Subjects had only a  $0.7\pm1.5$  kg weight gain.

Beyond our pilot study, literature regarding the use of EPA in treating bipolar disorder is extremely small (Stoll, 1999; Horrobin, 1999). The first study of omega-3 fatty acids for bipolar disorder, was a 4-month double blind placebo controlled study in which the authors added EPA+DHA, a total of 9.6g (6.2g and 3.4 g respectively) to ongoing

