We will enroll 90 subjects to allow for randomization of 30 subjects into each treatment arm of the study. The subject's first visit to the office consists of a meeting with a study clinician who explains the study, obtains informed consent, and administers an abbreviated form of the structured diagnostic assessment (45-90 minutes). After the evaluation with the study clinician, the subjects will undergo a neuropsychological assessment (45-60 minutes).

We anticipate that subjects may enter this trial following completion of/withdrawal from other Bipolar Disorder protocols in our office, and that there may be procedural overlap. So as to not burden subjects/parents/guardians with redundant time commitments, we will use the following data if previously collected:

- **Diagnostic Data:** If a subject has completed an evaluation with one of the study clinicians and/or the structured assessment within the previous 12 months prior to entrance into this study, they will not be asked to repeat any overlapping diagnostic procedures. However, the study clinician will review the interval time period to assess for clinically significant medical or psychiatric history, to ensure that the subject meets appropriate study entrance criteria.
- **Cognitive and Neuropsychological Testing:** If the subset of scales assessing intelligence (WASI or KBIT-2 for 5 year-olds) and cognitive functioning (select WISC tasks or WPPSI-III tasks for 5 year-olds) in the neuropsychological battery

have been completed within 12 months prior to entrance into this study, subjects will not be asked to repeat these procedures at screening/baseline.

• Screening Rating Scales: If a parent has completed the Child Behavior Checklist (CBCL), Social Responsiveness Scale (SRS), or the Behavior Rating Inventory of Executive Function – Parent Form (BRIEF) within the past six months as part of one of our screening protocols, we will not ask the parent/guardian to repeat these scales at screening/baseline.

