# Study Discontinuation

Subjects may drop at any time due to patient preference, physician decision, need for psychiatric hospitalization, or a poor response to treatment. Poor response to treatment will be measured by a CGI-bipolar score that is 2 points higher (more severe) than baseline for 2 weeks in a row or a YMRS score that is 30% higher than baseline for 2 weeks in a row, which may lead to drop from the study as determined by the clinician. Subjects with individual YMRS item scores of 8 on Item #8 (Content), or scores greater than 6 on Disruptive-Aggressive Behavior for 2 weeks in a row may be dropped from the study. Initial and emergent suicidality will be assessed weekly through administration of the Columbia Suicide Severity Rating Scale (C-SSRS). Subjects scoring 4 or higher will be dropped from the study. In addition, drop from study will occur at clinician discretion for worsening of clinical course, non-compliance with treatment or inability to tolerate study treatment.

Subjects will receive three months of optional pro bono clinical care visits (one monthly appointment over three months' time) at the completion of the study (or if they are required to discontinue for the above reasons) in which they will be seen by study staff. No research data will be collected at these follow-up visits. The three months of follow-up care are a courtesy that is offered to help find long-term care. Subjects will receive referrals to treaters in their communities.

Subjects who fail to return medication for two consecutive visits, fail to keep study appointments, or are non-compliant (less than 70% compliance for two weeks or longer) may be dropped from the study. These study subjects will be given a referral to treaters in their area.

If a subject becomes pregnant or is found to be abusing substances during the study, he or she will be discontinued from the study and given a referral as well. Since our target subject population is children 5-12 years of age, we do not anticipate that any participant will be at risk for pregnancy. However, a urine pregnancy test will be completed for female subjects ages 11-12 at screening. A physical exam, Tanner's staging, and parent report are collected at the screening as well visit to ascertain pubertal status. For subsequent study visits, pregnancy status is determined by verbal query of parent and/or subject or additional urine tests if needed.

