# C. Statistical Power

Power calculations were conducted with the statistical software package STATA. For repeated measures ANCOVA models, we assumed high correlation between follow-up assessments for the outcome of interest. Power was calculated for our study with 1 prerandomization baseline assessment and 12 follow-up assessments. For Hypotheses 1, comparing baseline to follow-up measures within group, the power to detect differences in YMRS or CDRS scores of 5 points (SD=10 points) is 0.86 with alpha set at 0.05. For differences in YMRS or CDRS scores of 7.5 points, power increases to 99%. For hypothesis 2 and Exploratory Hypothesis 3, testing differences between groups, the power to detect differences in YMRS or CDRS scores of 5 points (SD=10 points) is 0.93 with alpha set at 0.05 and 0.81 with alpha set at 0.01.

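### Section 9.A sets missing data aside and relies on last observation carried forward alone, although the exit rules make leaving depend on poor scores

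*Combined protocol and SAP*

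**What the plan says.** Section 9.A (Statistical Analysis) gives the premise, "Because this is a randomized trial following subjects over a short period of time missing data are not expected to impact our analyses", and then applies to every analysis the "last observation carried forward for subjects that do not complete the trial or are dropped from the study according to the exit criteria". No second method, sensitivity analysis or expected dropout rate appears anywhere.

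Other sections bear on the premise:

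- **Exit rules.** Section 7, Study Discontinuation, lists "a YMRS score that is 30% higher than baseline for 2 weeks in a row, which may lead to drop from the study", with a parallel CGI rule; both are left to the clinician. A C-SSRS score of 4 or more is a mandatory exit there and in section 9 (Safety). Section 12 (Protection Against Risk) words the poor-response exits as mandatory. Section 7, Concomitant Medications, treats rescue use beyond its limit as poor response and grounds for exit.
- **Pilot.** Section 1 reports that "of the 20 subjects recruited, there were only 4 drop outs due to ineffectiveness and none dropped out due to adverse events", in an 8-week open-label study. This trial lasts 12 weeks.
- **After exit.** Section 7 asks leavers for the final-visit tasks once, at discontinuation. The later courtesy visits collect no research data. Phone visits cover scheduling problems only.
- **Size and power.** Section 7: "We will enroll 90 subjects to allow for randomization of 30 subjects into each treatment arm of the study". Section 9.C: "Power was calculated for our study with 1 prerandomization baseline assessment and 12 follow-up assessments".
- **Endpoint.** Section 8: "The primary efficacy measures are the mean change from baseline to endpoint in the Young Mania Rating Scale (YMRS) total score", together with the same change in CDRS.

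**The concern.** Randomization and a short trial do not make missing data harmless when children leave because their scores are poor. Missingness then depends on the outcome, and LOCF treats the exit score as if it had been observed at week 12.

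Hypothesis 1 concerns change within each single-agent arm. A child who leaves early and would later have improved is credited with too little change. One who would have worsened further is credited with too much. For Hypothesis 2, early exit scores can dilute the arm difference and add noise. If exits differ by arm, the difference can move either way. A negative Hypothesis 2 could then reflect the imputation and not the treatments, and the plan contains no analysis that would show this.

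**Working it through.** **1. The plan's power figures.** For Hypothesis 2, section 9.C says "the power to detect differences in YMRS or CDRS scores of 5 points (SD=10 points) is 0.93 with alpha set at 0.05 and 0.81" (the latter at alpha 0.01). It calls the correlation high but gives no value.

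Change-score variance factor with 1 baseline and 12 follow-ups: f = (1 + 11r)/12 + 1 − 2r = (13/12)(1 − r).

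- With 30 per arm and r = 0.71 (back-solved), f = 0.314. The standard error is 10 × √0.314 × √(2/30) = 1.447, and 5/1.447 = 3.455.
- Power is Φ(3.455 − 1.960) = 0.933 at alpha 0.05 and Φ(3.455 − 2.576) = 0.810 at alpha 0.01. Both match.
- Power depends only on (1 − r)/n. So 27 per arm with r = 0.739, or 24 with r = 0.768, also gives 0.933 and 0.810.

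For Hypothesis 1, the stated 0.86 agrees with a one-sided one-sample formula: 5/(10/√30) = 2.739 and Φ(2.739 − 1.645) = 0.863. A two-sided paired formula with r = 0.6 gives 0.865. The method is not identified, so simulated Hypothesis 1 power is not set against 0.86.

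**2. Dropout anchor.** The pilot's 4/20 is 20%, with an exact 95% interval of 5.7 to 43.7%.

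**3. Simulation: assumptions.**

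- Three arms of 30; SD 10 (section 9.C); baseline mean 29 kept to 20-40 (pilot mean and entry limits); 12 weekly visits.
- Equal correlation of 0.71 or 0.75.
- True falls of 10, 10 and 15 points, either linear to week 12 or complete by week 4.
- Exit after each visit by a logistic hazard in change from baseline (slope 0.1 or 0.2 per point), set so that 20% of a single-agent arm has left by week 8 (23-26% before week 12). The exit score is observed.
- Complete data and LOCF: three-arm ANCOVA with baseline. Mixed model: unstructured covariance.

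Hypothesis 2 power, alpha 0.05, 20% gone by week 8:

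| Onset and contrast | Complete | LOCF | Mixed model |
|---|---|---|---|
| Linear, week 12 | 0.76-0.83 | 0.50-0.58 | 0.70-0.76 |
| Complete by week 4, 12-visit average | 0.92-0.96 | 0.73-0.83 | 0.90-0.96 |
| Complete by week 4, week 12 | 0.76-0.83 | 0.66-0.73 | 0.69-0.76 |

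The mixed-model column was obtained only under equal correlation, with no child returning after exit.

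**4. Within-arm change.** A true 10-point fall shows as about 7.3-8.9 under LOCF and 9.9-10.1 under the mixed model with baseline as first response. The sign of the LOCF error reverses if leavers would have ended worse than their observed course predicts by more than (10 − fall shown)/(share leaving), about 5 to 12 points across the scenarios.

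**5. Fewer or unequal exits.**

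- YMRS 30% rule alone, always applied, every arm improving: 1-6% leave. LOCF gives 0.91-0.94 against 0.94-0.95 (early effect, 12-visit average) and 0.62-0.71 against 0.75-0.81 (linear, week 12).
- Same rule, no single-agent effect, immediate 5-point benefit of the combination: about 17% against 4% leave, and LOCF enlarges the week-12 difference from 5.0 to 5.7.
- No true difference and a common exit rule: LOCF type I error is 0.045-0.057.

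**6. Contrast, with nobody missing.** Week-12 ANCOVA has standard error 10 × √(1 − r²) × √(2/30), which is 1.818 at r = 0.71 and 1.708 at r = 0.75. Power by noncentral t (86 df) is 0.776 and 0.825, already below 0.93.

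**The case against.** The best defence is that the large losses rest on an assumed exit hazard. The only fully quantified rule on the YMRS total removes few children when all arms improve, and with an early effect LOCF then costs almost nothing. In one check, with an effect present from week 1, about 20% leaving largely independently of score, and a 12-visit average, power was 0.95 against 0.97. The pilot rate comes from 20 children in an uncontrolled study. Moreover, if the target is status at the last assessment on treatment, the exit score is the outcome itself and LOCF is not biased for it. All of this stands. It limits the size of the concern and shows that the plan must name its target. It does not rescue a premise contradicted by the exit rules, or the absence of any sensitivity analysis.

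A reader might also infer more than the documents support:

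- **That the stated powers prove no loss was allowed for.** They cannot, because an unstated correlation lets 24, 27 or 30 per arm fit equally well. What can be said is that no allowance is stated.
- **That LOCF will lower power for Hypothesis 2.** It can. In some cases the loss is negligible, and in one the difference grew.
- **That false positives are inflated.** Not under a common exit rule. Inflation (0.08-0.10) appeared only when score-independent exits of 10% against 30% by arm were assumed.
- **That the gap between 0.93 and 0.76-0.83 at week 12 is due to LOCF.** It exists with complete data. It comes from the choice between change to endpoint (section 8) and the 12 follow-up assessments (section 9.C).

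**Conclusion.** The point holds in limited form. Section 9.A rests on a premise that the document's own exit rules and pilot undercut, and it offers one untested method. For the outcome had treatment continued, LOCF can misstate within-arm change in either direction, can reduce Hypothesis 2 power, and can shift the arm difference either way if exits differ by arm.

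At the pilot's exit rate, the illustrative cost for Hypothesis 2 is roughly a quarter in power for a slowly building effect read at week 12. It is roughly 0.1 to 0.2 for an early effect averaged over visits. These sizes depend on the assumed correlation, onset and exit mechanism, none of which the documents give. Confidence is high that the method needs changing and moderate on the figures. This is a cheap improvement.

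**What to change.** In section 9.A:

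1. Delete the sentence that dismisses missing data.
2. Make the primary analysis a likelihood-based mixed model for repeated measures on all observed weekly scores, including the exit assessment, without imputation. For Hypothesis 2 fit arm, visit, arm-by-visit, baseline and baseline-by-visit. For Hypothesis 1 take within-arm change from a model with baseline as the first response.
3. Specify unstructured covariance with simpler fallbacks in a pre-stated order. With 90 children it has 12 × 13/2 = 78 parameters for Hypothesis 2 and 13 × 14/2 = 91 for Hypothesis 1.
4. State the target: the outcome had treatment continued, or exit for poor response counted as failure. The mixed model estimates the first; the second needs its own analysis rule.
5. Name one primary contrast, reconciling section 8 with section 9.C, and restate power for it with an explicit dropout assumption.
6. Keep LOCF as a sensitivity analysis. Add a delta-adjusted (tipping-point) analysis that makes post-exit values progressively worse and reports the shift at which the conclusion changes.
7. Tabulate exits by arm, week and reason.

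The sections that word the same exits as discretionary in one place and mandatory in another should also be reconciled, so that exits can be classified.

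Cost: modest programming in the software already named, with no new visits or data. The stated power will probably look less favourable. Missing at random cannot be tested, which is why the tipping-point analysis is needed. For an early effect read at week 12 the gain over LOCF is only about 0.03 in power.
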